We carried out spirometry-controlled CT scans at baseline, one year and two years after the introduction of LUM/IVA in 35 children aged 6-11, homozygous for the F508del mutation. Standardization of the scanner output, protocol and data transfer was managed through the LungAnalysis team. Images were scored using the Perth Rotterdam Annotated Grid Morphometric Analysis (PRAGMA) scoring system. Over the course of 2 years on LUM/IVA, while improvements were seen in the mean air trapping scores, bronchiectasis scores increased (Table 2). These data suggest that LUM/IVA can improve air trapping but does not prevent the progression of bronchiectasis in these young children with CF. The data were presented at NACFC 2021 and currently being submitted for publication. Ongoing work is examining the airway wall and artery dimensions in detail in these sans using specifically developed proprietary software in an automated fashion.

PRAGMA Score	E	Baseline		Year 1			
	Mean (95% CI) n=32		Mean (95% CI) n=32	Mean (p-value	
% Bronchiectasis	0.82	(0.48 - 1.16)	0.85	(0.51 - 1.19)	1.24	(0.89 - 1.60)	0.005
% Disease	2.78	(2.12 - 3.45)	2.46	(1.79 - 3.14)	2.25	(1.55 - 2.94)	0.138
% Trapped Air	0.13	(0.09 – 0.16)	0.10	(0.07 – 0.14)	0.07	(0.03 – 0.11)	0.016
% Mucous plugging	0.57	(0.31 – 0.83)	0.28	(0.01 - 0.54)	0.33	(0.04 - 0.62)	0.221

Table 2. Change from baseline in PRAGMA CT scores in 35 children homozygous for the F508del mutation, aged 6-11 on treatment with Lumacaftor/Ivacaftor.

PRELIMINARY data from RECOVER Parent Study

Despite unexpectedly accelerated approval of ETI in Europe in 2020 and a global pandemic, we have reasonable levels of recruitment to date (85% target) and retention of subjects in the first phase (12+) of RECOVER. One-year outcomes were presented at ECFS 2022 (Table 3 below) and Phase 2 of RECOVER (6-11) is continuing to recruit subjects. Figure 4 below shows significant differences in baseline (pretreatment) values for FEV1 and LCI in the 12+ and 6-11 groups, underlining the 'normalization' of LCI in younger children

P.I. [name]

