In this multi-centre longitudinal study of subjects starting on ETI we will be examining many different outcomes, and so sample size requirements are different for different aspects. Patients will be recruited to the study up to a cap of 254 participants. On the basis of the phase two trials of ETI(57), we are expecting a significant treatment effect in line with what was previously seen with Ivacaftor treatment in individuals with a gating mutation, and in excess of what was seen with Lumacaftor/Ivacaftor in individuals homozygous for F508del. Our sample size is higher than we expect to be required for most outcomes where data exists (see tables 11, 12, 13 below). We have aimed high deliberately for a number of reasons. Firstly, clinical research naturally carries risks in terms of adequacy of data collection. Secondly, we are keen to ensure that outcome measures can be cross referenced between each other and with previously collected, yet to be collected and data and samples. This will require excess power. With missing or incomplete samples across different outcome measures, complete datasets on a core number of individuals will necessitate collection in a larger cohort. Thirdly, this study represents a unique opportunity, which may not be replicated, to collect this data, and promises very significant insights into CF disease pathogenesis and response to therapies. In light of this, a large sample size with adequate sample collection we feel is important. Where data is available, we have performed sample size calculations (table 10). Where data is not available, we present a summary of key studies and evidence in the area.

Power and sample size calculations were produced for LCI as a main primary endpoint, using the GLMPOWER procedure in SAS 9.3 (Table11, Figure 5). A range of scenarios were considered for standard deviation from 2 (expected) to 3 (conservative) and power was computed for F/F participants only and for F/F and F/M participants combined. We estimated a conservative treatment effect at 1 unit of improvement in LCI (as seen with lumacaftor/ivacaftor), and an expected treatment effect at 2 unit of improvement in LCI (as seen with lvacaftor in gating mutations).

Group	Sample Size	Std Dev	Power (1 unit)	Power (2 unit)
F/F only	166	2	91.9%	99.4%
F/F & F/M	201	2	96.4%	99.9%
F/F only	166	2.5	76.6%	94.8%
F/F & F/M	201	2.5	85.3%	98.0%
F/F only	166	3	61.0%	84.7%
F/F & F/M	201	3	70.8%	91.7%

[figure not shown]

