Figure 5 Sample size versus power for LCI. Power calculations are for an absolute difference of A) 2 LCI unit and B) 1 LCI unit between baseline and 1 year, assuming a conservative estimate for standard deviation of 3.

Endpoint	Reference Study	Comments
LCI	[name] et al(76), [name] et al(56)	Significant improvement in LCI was seen with Ivacaftor with 20 subjects and Orkambi with 206 participants
PRAGMA CT score	Rosenow et al(130)	Sample size estimates in this paper suggested 100 children required to see a 50% reduction in %disease over 3 years and 76 for an approximate halving of bronchiectasis progression over 3 years. This is in very young children with mild disease.
FeNO	[name] et al(89)	A significant increase in FeNO was seen with 15 subjects on Ivacaftor
Liver disease parameters	Rowland et al.(40)	Limited relevant data available. 10 year follow up in 84 individuals revealed significant differences in mortality. Unpublished data on 522 individuals, some of whom will be part of RECOVER has again shown significant changes in status over time and mortality.
GI inflammation	Ooi et al (32)	Significant reductions in calprotectin and M2PK seen in 16 individuals on Ivacaftor
Abdominal symptoms	Tabori et al (29)	114 subjects were studied. Significant differences in abdominal symptom scores were seen between individuals with PS and class 4 or 5 CFTR mutations and those with class 2 and PI suggesting that reported symptoms may be relatable to CFTR function in a cohort of this size

P.I. [name]

050 D		
CFQ-R	Keating et al (59)	Total recruitment was 123 participants (F508del homozygotes
		and heterozygotes with differing dose levels. Between group
		comparisons using 7-21 subjects per group showed
		significant improvements in CFQ-R compared to controls
Airway	Hisert et al (12)	Significant and sustained reductions in sputum inflammatory
Inflammation		markers were seen in 12 subjects after the initiation of
		Ivacaftor
Nasal	Muller et al(23),	Nasal inflammation in 19 individuals after IV antibiotic therapy
inflammation	McCormick et	showed a trend to improvement. Ivacaftor treatment in 153
	al(24)	individuals was associated with significant improvements in
		nasal symptom score. Data for nasal inflammation and CFTR
		modulator use is not available.
Sweat Chloride	Keating et al (59)	Total recruitment was 123 participants (F508del homozygotes
onout onionao	roading of al (00)	and heterozygotes with differing dose levels. Between group

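### Table 11 states LCI power at 166 and 201 participants with no allowance for missing LCI; at the completion seen in the protocol's own interim data, Table 6 enrolment would not yield those numbers

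*Protocol*

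**What the plan says.** Sample Size and Power for the Parent Study (Statistical Analysis) reports: "Power and sample size calculations were produced for LCI as a main primary endpoint", with SAS GLMPOWER as the software. The SD scenarios are described as follows: "A range of scenarios were considered for standard deviation from 2 (expected) to 3 (conservative". The conservative effect is 1 LCI unit and the expected effect 2 units. The first rows of Table 11 read "F/F only 166 2 91.9% 99.4" and "F/F & F/M 201 2 96.4% 99.9" (the last two figures are power for 1 and 2 units). The Figure 5 legend identifies the contrast: "Power calculations are for an absolute difference of A) 2 LCI unit and B) 1 LCI unit between baseline and 1 year".

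Missing data are acknowledged in words: "With missing or incomplete samples across different outcome measures, complete datasets on a core number of individuals will necessitate collection in a larger cohort". No LCI completion rate is given. Other outcomes do have explicit rates: sputum 90/80/70/60% (Risks in Airway Inflammation data collection) and stool 85/80/70/60% (Risks with GI Data Collection).

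Table 6 plans 74+96=170 F/F and a further 26+41=67 F/M, so 237 for the two groups together, within a cap of 254. The stool section uses 201 as a number recruited.

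On the first phase the protocol reports that "we have reasonable levels of recruitment to date (85% target) and retention of subjects in the first phase (12+) of RECOVER". Table 3 gives the LCI counts: 82 at baseline (N=114), 83 at 6 months (N=103) and 49 at 12 months (N=90).

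**The concern.** A power figure applies to the number of people who contribute to the contrast. Table 11 uses 166 and 201 as they stand. Set against Table 6 they leave headroom of 4 in 170 (2%) for F/F and 36 in 237 (15%) for F/F and F/M. Those two figures do not look like one missing-data allowance applied to nested groups. They look more like an enrolment plan that was later changed without updating the power table.

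The protocol's own data suggest that LCI loss is larger than either margin. It is also largely specific to LCI. At baseline, ppFEV1 is available for 114 of 114 people and FeNO for 112 of 114, against 82 for LCI. At 12 months, FeNO is available for 90 of 90 and ppFEV1 for 87 of 90, against 49 for LCI. (At 6 months the pattern differs: ppFEV1 82 and LCI 83 of 103.)

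At stake is the stated power for an endpoint that the protocol calls main primary.

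**Working it through.** **1. Can Table 11 be reproduced?** The model, alpha and sidedness are not stated, so two-sided 5% is assumed. For n=166 and SD 3, Table 11 prints 61.0% (1 unit) and 84.7% (2 units). The candidates give:
- paired test, SD of change: 99.0% and about 100%
- two independent samples of 166 each: 85.7% and about 100%
- two groups of 83: 56.9% and 99.0%

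None fits both columns. A one-sided test, a 2:1 split and alpha 0.01 do not reproduce the table either.

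The two columns also disagree with each other. The implied noncentrality is z(power)+1.96. At n=166 and SD 2.5 this is 2.686 for 1 unit (76.6%) and 3.586 for 2 units (94.8%), a ratio of 1.335. Doubling the effect must double it. The ratio is 1.33–1.34 in all six rows.

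**2. LCI completion in Table 3.**
- Baseline: 82/114 = 71.9%
- 6 months: 83/103 = 80.6%
- 12 months: 49/90 = 54.4% of those counted, or 49/114 = 43.0% of those enrolled

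At most 49 people can have both a baseline and a 12-month LCI.

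**3. Applied to Table 6 enrolment.**

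| Completion rate | F/F (170) | F/F and F/M (237) |
|---|---|---|
| 80.6% (6 months) | 137 | 191 |
| 71.9% (baseline) | 122 | 170 |
| 54.4% (12 months, of 90) | 92 | 129 |
| 43.0% (12 months, of 114) | 73 | 102 |
| Table 11 | 166 | 201 |

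Every row falls below Table 11, including the most favourable. The 12-month rows are upper bounds on baseline to 1-year pairs, because some people with a 12-month LCI may lack a baseline one.

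**4. Power if the SD is that of the paired change.** Noncentral t with df = n−1 and noncentrality = Δ√n/SD. For Δ=1 and SD 3:
- n=73: √73/3 = 2.85, power 80.2%
- n=102: √102/3 = 3.37, power 91.5%

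For Δ=2, power is near 100% at both.

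**5. Power on Table 11's own 1-unit scale.** Noncentrality is scaled by √(m/n), and power = Φ(scaled value − 1.96). For SD 2.5:
- F/F: 2.686×√(73/166) = 1.781 gives 43%; 2.686×√(92/166) = 2.00 gives 52%. Printed: 76.6%.
- F/F and F/M: 3.009×√(102/201) = 2.144 gives 57%; 3.009×√(129/201) = 2.411 gives 67%. Printed: 85.3%.

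Step 5 shows only what the printed column would imply. Given step 1, it is not a valid estimate of power.

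**The case against.** A reader might infer that 166 and 201 LCIs can never be analysed. The documents do not support that. Table 3 is an extract of available cleaned data from the 12+ phase only, collected during a pandemic and an accelerated approval. Only 90 of 114 people are counted at 12 months, so 43% may mix people not yet due or not yet cleaned with tests that were missed. Nothing in the protocol shows that children aged 6–11 will have the same rate.

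A reader might also infer that Table 11 claims full data on 166 and 201 people, or that these numbers appear nowhere as enrolment. The table says only sample size, and the stool section uses 201 as a recruitment count. What can be said is that no LCI completion rate was applied and that neither number agrees with Table 6.

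Other mitigations are real. A second pre-treatment LCI is scheduled at −3 months. The final parent-study LCI analysis is at two years, with further LCIs at 18 and 24 months. Mixed models and multiple imputation are planned. These may recover part of the loss, but they do not turn the observed counts into 166 or 201, and the planned complete-case analyses depend directly on the counts.

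Finally, Table 3 already reports p<.0001 for LCI at baseline versus 6 months, and the expected 2-unit effect is well powered on a paired reading. This stands: the point concerns the stated basis of power, not whether an effect will be found.

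**Conclusion.** The point holds in a limited form. Table 11's sample sizes have no LCI completion rate behind them, disagree with Table 6, and are not attainable from Table 6 enrolment at the completion so far observed: about 122 and 170 at the baseline rate, and 73–92 and 102–129 at the 12-month rates. This assumes that the interim 12+ rates persist and also apply to the 6–11 phase, which further cleaning may change.

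The loss of power cannot be fixed at one figure because the SD is undefined. On the paired-change reading, 1-unit power at SD 3 stays at about 80–92% for 73 to 102 pairs. On the table's own 1-unit scale at SD 2.5 it would drop to about 43–52% (F/F) and 57–67% (F/F and F/M), but that scale is internally inconsistent. If the SD is that of the LCI level, the values in Table 3 (3.829, 3.689 and 4.274) already exceed the 3 labelled conservative. The table needs re-running in any case.

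**What to change.** Re-run Table 11 as follows:
- State the model, alpha and sidedness, and whether the SD is of the LCI level or of the within-person change.
- Take n as Table 6 enrolment (170 and 237) times an expected LCI completion rate for the baseline to 1-year contrast. Show it as a range, for example 43% to 81% (about 73–137 F/F and 102–191 F/F and F/M), and update it when cleaning of the first phase ends.
- Replace 166 and 201 in Table 11, and reconcile the same numbers in Table 13 and the 201 in Risks with GI Data Collection with Table 6.
- Check that the 1-unit and 2-unit columns come from the same model.

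The cost is re-running one table and stating power that is probably less favourable. No extra patients or procedures are needed.

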Table 6 outlines projected recruitment targets for both groups. Advanced testing will be offered to all participants to the cap in table 6, on the basis of fully informed consent. Progress in recruitment to both groups will be monitored by the project manager and monitor.

	F/F		F/M		F/G		TOTALS		S
	6-		6-		6-		6-		
Ages	11	12+	11	12+	11	12+	11	12+	All
ADVANCED	47	60	17	26	17	0	64	86	150
STANDARD	27	36	9	15	0	0	36	51	87

Total 74 96 26 41 17 0 117 137 254	Total	74	96	26	41	17	0	117	137	254	
------------------------------------	-------	----	----	----	----	----	---	-----	-----	-----	--

Table 6. Projected recruitment to standard and advanced testing arms for parent study.

Primary and Secondary Outcomes

The primary outcome measure for this study is the absolute change from base line values and CT scores.

The secondary outcome measures are as follows;

- height/weight/BMI
- FEV1
- Airway microbial culture
- Airway microbiome determination
- Nasal Lavage inflammatory markers
- Nasal microbiome determination
- Exhaled Nitric Oxide
- Liver function testing
- Liver ultrasound Liver
- Examination score
- Sputum inflammatory markers
- Sputum microbiome determination
- Stool inflammatory markers
- Stool microbiome determination
- Sweat Chloride
- Genetic modifiers of CF phenotype
- Abdominal symptom score
- CFQ-R
- Treatment Adherence
- Medication Pick up rates

Core Data to be Collected

Eligibility assessment

Prior to study enrolment, the investigator will assess subject eligibility. This will include reviewing the subject's current medication and medical history in detail to ensure no exclusion criteria are met and all inclusion criteria are met. As part of the eligibility assessment, a urine pregnancy test (CE marked) must be conducted in female participants considered of childbearing potential (WOCBP). WOCBP are defined as females that are fertile, following menarche, until becoming post-menopausal unless permanently sterile. Permanent sterilisation methods include hysterectomy, bilateral salpingectomy and bilateral oophorectomy. A postmenopausal state is defined as no menses for 12 months without an alternative medical cause. A negative test must be produced prior to enrolment and documented within the subject's medical records.

Demographic data

Core demographic data will be collected on all individuals including genotype, sex, date of birth, CF centre and medications.

Sweat Chloride

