FEV1 measured by spirometry is the most widely used evaluation of lung function in CF. As FEV1 has been used as the primary endpoint in numerous clinical trials in CF to date, it is important that the rate of FEV1 change is recorded and analyzed as a secondary endpoint in this study. Spirometry will be carried out on each subject at three monthly intervals throughout the duration of the parent study, and annually during the extension study as part of routine clinical care. Spirometry will be performed according to the American Thoracic Society (ATS) guidelines(125). Spirometry values collected as part of routine clinical care will be used for this study, rather than repeating this testing specifically for the purposes of the study. Other spirometric measures such as FVC, FEV1/FVC and FEF25-75 will be collected for inclusion in later analyses. The absolute and relative changes and rate of change in % predicted FEV1 (GLI – Global Lung Initiative) will be assessed from baseline to annual subsequent follow up periods.

Lung Clearance Index

LCI will be performed with the Exhalyzer D multiple breath washout device (Eco Medics AG, Duernten, Switzerland). The test itself is usually completed within twenty to thirty minutes (the test takes longer the more airway disease is present) and will be performed according to the European Respiratory Society / American Thoracic Society consensus statement 2013 on the performance of multiple breath inert gas washout(126).. MBW operators will be trained and certified by the team at Guy's and St Thomas' NHS Foundation Trust) under the supervision of [name]. Centralized over-reading will be completed at the RBH centre. All tests will be performed in replicate, and average values calculated for acceptable trials. LCI will be performed pre-bronchodilator in all subjects. LCI will be performed three months prior to the baseline visit and then at baseline and at 6 monthly intervals subsequently for the parent study, and annually during the extension study..

Analysis plan

The primary endpoint for LCI for the parent study will be the absolute difference in LCI in children on ETI compared the pre-treatment baseline. An interim analysis will be completed after one year of treatment, and a final parent study analysis at the end of two years. Subsequent annual and multi-annual change in LCI will be assessed during the extension study.

Risks with FEV1 and LCI Data Collection

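### The two LCI power columns in Table 11 contradict each other, and neither fits the within-person change that is the declared LCI endpoint

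*Protocol*

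**What the plan says.** Under Sample Size and Power for the Parent Study, the protocol states: "Power and sample size calculations were produced for LCI as a main primary endpoint, using the GLMPOWER procedure in SAS 9.3". Two effects are considered. The first is described as: "We estimated a conservative treatment effect at 1 unit of improvement in LCI (as seen with lumacaftor/ivacaftor"). The second is "an expected treatment effect at 2 unit of improvement in LCI". On variability: "A range of scenarios were considered for standard deviation from 2 (expected) to 3 (conservative"). Table 11 gives power for both effects at SD 2, 2.5 and 3, for N = 166 (F/F) and N = 201 (F/F and F/M combined).

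The caption of Figure 5 defines the contrast: "Power calculations are for an absolute difference of A) 2 LCI unit and B) 1 LCI unit between baseline and 1 year". The Analysis plan under Specific Aim 1 defines the LCI endpoint in the same way, as the "absolute difference in LCI in children on ETI compared the pre-treatment baseline".

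The section does not give alpha or sidedness. It does not say whether the SD is that of LCI at one visit or of the change, gives no within-person correlation, and does not say whether N is a total, a number per visit or a number of pairs.

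**The concern.** With N, SD and design held fixed, the noncentrality of the test is proportional to the effect. Moving from 1 to 2 units should therefore raise power steeply. In Table 11 it rises too little: at SD 3 and N = 166 it goes only from 61.0% to 84.7%. The powers are also far below what a before-and-after comparison of well over 150 people would give for these effects.

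This is the only formal power calculation for LCI, and the section cites Tables 11 to 13 when it says the sample exceeds what most outcomes need. If the labels or the design behind the table are wrong, a reader cannot tell what LCI effect the study can detect.

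**Working it through.** **Inputs.** N, SD, effects and powers are from Table 11. Alpha is assumed two-sided 0.05. The table supports this: implied noncentrality times SD is constant across SDs at this alpha (N = 166, 1-unit column: 3.378 × 2 = 6.76; 2.702 × 2.5 = 6.76; 2.252 × 3 = 6.76).

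**Step 1: noncentrality implied by each stated power.** The noncentral t (N − 2 df) was solved for each cell.

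| N | SD | Stated power, 1 / 2 units | Implied noncentrality | Ratio |
|---|---|---|---|---|
| 166 | 2 | 91.9 / 99.4% | 3.378 / 4.499 | 1.332 |
| 201 | 2 | 96.4 / 99.9% | 3.777 / 5.075 | 1.343 |
| 166 | 2.5 | 76.6 / 94.8% | 2.702 / 3.607 | 1.335 |
| 201 | 2.5 | 85.3 / 98.0% | 3.024 / 4.033 | 1.334 |
| 166 | 3 | 61.0 / 84.7% | 2.252 / 3.001 | 1.332 |
| 201 | 3 | 70.8 / 91.7% | 2.520 / 3.361 | 1.334 |

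Hand check of the fifth row by normal approximation: z(0.610) + 1.96 = 2.24 and z(0.847) + 1.96 = 2.98; 2.98 / 2.24 = 1.33. The required ratio is 2. Doubling that row's 1-unit noncentrality (2 × 2.252 = 4.504) would give 99.4% power for 2 units, not 84.7%.

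**Step 2: what reproduces the table.** Write the variance of the contrast as k × SD² / N, so noncentrality = effect × √N / (SD × √k). Two settings reproduce all 12 cells within 2 percentage points:

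- effects 1.5 and 2 with k = 8 (two groups sharing N, change scores with variance 2 × SD²);
- effects 0.75 and 1 with k = 2 (the two visits as independent samples of N each).

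They are almost indistinguishable because 1.5/√8 = 0.75/√2 = 0.530 and 2/√8 = 1/√2 = 0.707. At N = 166, SD 3, they give 62.0 / 85.5% and 62.2 / 85.7%. No layout tried reproduced the 1-unit column with an effect of 1; the nearest (k = 4) missed by more than 2 points in every row.

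**Step 3: the declared contrast.** For a paired comparison, noncentrality = effect × √N / SD_change, with SD_change = SD × √(2(1 − ρ)) if the tabulated SD is a visit SD and ρ the within-person correlation. Example for 1 unit, N = 166, SD 3:

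- SD is the SD of change: 12.884 / 3 = 4.295, power 98.95%.
- SD is a visit SD, ρ = 0: 12.884 / (3 × 1.414) = 3.037, power 85.5%.

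| N | SD | Stated, 1 unit | Paired, SD of change | Paired, visit SD, ρ = 0 |
|---|---|---|---|---|
| 166 | 2 | 91.9% | >99.9% | 99.5% |
| 201 | 2 | 96.4% | >99.9% | 99.9% |
| 166 | 2.5 | 76.6% | 99.9% | 95.2% |
| 201 | 2.5 | 85.3% | >99.9% | 97.9% |
| 166 | 3 | 61.0% | 98.95% | 85.5% |
| 201 | 3 | 70.8% | 99.7% | 91.4% |

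Zero correlation gives the lowest power among non-negative correlations. For 2 units, paired power exceeds 99.9% in every row on both readings.

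**Step 4: could an unstated correlation rescue the table?** At N = 166, SD 3, the stated 1-unit power needs an SD of change of 5.75, so ρ = 1 − 5.75² / (2 × 9) = −0.84. The stated 2-unit power needs 8.64, so ρ = 1 − 8.64² / 18 = −3.15, which is impossible. The other rows give about −0.8 and −3 as well.

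**The case against.** The strongest reply is that little depends on the error. The section caps recruitment at 254 and justifies a large cohort by missing data, cross-referencing of outcomes and the rarity of the opportunity. For a paired comparison the printed powers are too low, so the mistake is conservative. Table 3 already reports a significant interim LCI change in the 12+ group. All of this stands, and it makes the point a correction of a stated figure rather than a threat to the study. It does not remove the contradiction between the columns.

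Three stronger readings are tempting and are not supported:

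- **That the 1-unit column was computed for 1.5 units.** This follows only if the 2-unit label is right. The CT %disease row of Table 13 lends it some weight: an effect of 1.31 (half of 2.62) with SD 2.59 and k = 8 gives about 63% and 71%, against a stated 62.0% and 71.8%. Other Table 13 rows imply a k of about 6 (nasal IL-8), 10 (FeNO), 12.5 (abdominal score) and 20 (sweat chloride), so no common layout is established.
- **That true 1-unit power is as low as 32% to 39% at SD 3.** Halving the 2-unit noncentrality gives such figures, but they belong to a two-arm layout that the study does not use.
- **That only 49 pairs are available.** Table 3 shows 49 LCI values at 12 months in interim data for ages 12 and over. That is a visit count, not a pair count, and it excludes the 6-11 cohort.

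Powering at 1 year is not an error in itself, since the Specific Aim 1 analysis plan includes a one-year interim analysis.

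**Conclusion.** The point holds as an error in a stated figure. The two columns of Table 11 rest on effects in ratio 3:4 and are labelled 1:2, so at least one label is wrong. Neither column fits the within-person contrast in the Figure 5 caption and the Specific Aim 1 analysis plan.

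For that contrast the table understates 1-unit power in every row. The largest gap is at N = 166, SD 3: 61.0% stated against 85.5% (visit SD, zero correlation) or about 99% (SD of change). This rests on two-sided 0.05, a non-negative within-person correlation, and 166 or 201 evaluable pairs; with fewer pairs power would be lower. A reader might conclude that the study is underpowered for LCI. The document does not support that.

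**What to change.** Recompute Table 11 and Figure 5 as a paired (one-sample change) calculation, with the columns labelled by the effects actually used. State:

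- alpha and sidedness;
- the SD of change, or the visit SD with a within-person correlation, shown over a range;
- the time point;
- N as the expected number of evaluable baseline and follow-up pairs.

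Do not replace the 1-unit column with figures from a two-arm layout, and do not present the interim count of 49 as a number of pairs. The cost is one recalculation and an amendment to one table and one figure. No extra patients are needed.
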